8.5.2. Pharmacokinetic Evaluation

- The following PK parameters will be calculated for Day 1 and Day 7 from the individual plasma concentration-time data of diclofenac for each intervention by non-compartmental analysis using Phoenix® WinNonlin® Version 7.0 or higher (applying linear trapezoidal linear/log interpolation method for calculation of AUC), see [Table 8](#).
- or definition of PK parameters [Section 10.6](#).

Table 8: Pharmacokinetic Parameters for diclofenac in plasma

| | Day 1 | Day 7 |
|------------------------------------|---------------------|---|
| Main PK Parameters | | |
| | - | AUC ₀₋₂₄ |
| Additional PK Parameters | | |
| | AUC ₀₋₂₄ | - |
| | C _{max} | C _{max} |
| | - | C _{min} |
| | | Swing = (C _{max} - C _{min}) / C _{min} |
| | C _{ave} | C _{ave} |
| | t _{max} | t _{max} |
| | - | t _{min} |
| | - | PTF |
| Racc(AUC 0-24h) Day 7 versus Day 1 | | |

- Individual PK parameters will be calculated using actual sampling times. A pre-dose sample will always be considered as if it had been taken simultaneously with the intervention administration. If there should have been any deviations in post-dose sampling, the actual sampling times relative to drug administration will be used, unless stated otherwise. Missing data will not be replaced or imputed in any way.

- For calculation of PK parameters, concentrations below the lower limit of quantification (LLOQ) will be treated as zero.
- AUC will be regarded as unreliable if more than two consecutive results are missing or if the concentrations were quantifiable for fewer than 5 timepoints. C_{max} and t_{max} will be regarded as unreliable if the maximum was observed preceding or following a sample with missing data. In case of multiple peaks, C_{max} and t_{max} refer to the highest measured concentration even if there should be earlier peaks. In case of two or more samples with the same concentration (as supplied by the analyst), t_{max} refers to the earlier of these.
- Unreliable parameters will be listed and flagged accordingly and set to missing for calculation of descriptive statistics and statistical analysis. If a PK parameter is unreliable for more than 20% of the subjects, this parameter will additionally be evaluated as sensitivity analysis including the reliable cases.
- More details will be provided in the SAP.

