9.2. Analysis Sets

For purposes of analysis, the following analysis sets are defined:

| Analysis Set | Description |
|----------------|--|
| Screening Set | All subjects screened. |
| Randomized Set | All subjects randomly assigned to study intervention. |
| Safety Set | All subjects randomly assigned to study intervention and who receive at least 1 dose of study intervention. Subjects will be analyzed according to the intervention they actually received. This analysis set will be used for the analysis of safety. |
| PK Set | This analysis set is a subset of the Safety Set and includes all subjects who complete at least one period without any findings/events likely affecting PK. This analysis set will be used for the analysis of PK. |

Finding/events potentially affecting PK will be pre-specified in a deviation manual.

The final decision to exclude complete subjects or single periods of subjects from the PK analysis will be made during a DRM prior to database lock. The respective meeting minutes will be signed together with the Sponsor.

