9.3.3. Pharmacokinetic Analyses

- All PK analyses will be performed on the PK Analysis Set, if not stated otherwise.
- Concentration-time courses and PK parameters will be tabulated by intervention.
- The following statistics will be calculated for each of the sampling timepoints: number of cases/ measurements (denoted as “n”), geometric mean and geometric coefficient of variation (CV, in %), arithmetic mean, standard deviation (SD) and CV (in %), minimum, median, maximum.
- Individual and arithmetic mean plasma concentration versus time curves (using the actual sampling times for individual plots and the scheduled sampling times for mean plots) will be plotted by intervention using both linear and log-linear scale.

Further analysis for the primary PK parameter AUC₀₋₂₄:

- In order to achieve a better approximation to a normal distribution, the pharmacokinetic parameters AUC₀₋₂₄ on Day 1 and Day 7 will be logarithmically transformed. Afterwards, they will be evaluated statistically using ANOVA with INTERVENTION, PERIOD, SEQUENCE and SUBJECT(SEQUENCE) as fixed effects. Least-squares (LS) means, LS intervention difference, and 90% confidence intervals (CI) for the intervention differences on the log-scale will be obtained for AUC₀₋₂₄ on Day 1 and on Day 7. The results will be back-transformed to the original scale by exponentiation to provide geometric least-square means, point estimate of the geometric mean ratio (Test/Reference) and its corresponding 90% CI.
- Only subjects that have a valid AUC₀₋₂₄ in both periods will be included in the above-mentioned model.

Further analysis for the secondary PK parameter C_{max}:

- The same ANOVA model as described for AUC₀₋₂₄ above will be provided for the secondary parameter C_{max}.

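### For the AUC0-24 ratio, the sensitivity analysis in Protocol 8.5.2 uses the same reliable values as the main analysis and cannot show whether the exclusions matter

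*Protocol*

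**What the plan says.** Protocol section 8.5.2 gives the rules for unreliable parameters. An AUC is unreliable if more than two consecutive results are missing, or "if the concentrations were quantifiable for fewer than 5 timepoints". Cmax and tmax have a separate rule, based on missing samples next to the maximum. The consequence is: "Unreliable parameters will be listed and flagged accordingly and set to missing for calculation of descriptive statistics and statistical analysis".

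The next sentence sets a condition, "If a PK parameter is unreliable for more than 20% of the subjects", and states what then follows: "this parameter will additionally be evaluated as sensitivity analysis including the reliable cases". The section closes by leaving further details to the SAP.

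Section 9.3.3 fits an ANOVA to log AUC0-24 with intervention, period, sequence and subject within sequence, all as fixed effects. Only subjects with a valid AUC0-24 "in both periods will be included in the above-mentioned model". The PK Set in section 9.2 is wider: it "includes all subjects who complete at least one period without any findings/events likely affecting PK".

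**The concern.** A sensitivity analysis should change something that the main analysis fixed. Here the main analysis has left the unreliable values out, and the additional analysis is defined by the values that were kept. Nothing else in the protocol brings the flagged values back.

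The condition makes this matter more. The analysis runs only when more than one subject in five has an unreliable value, which is when a reader needs to know whether the exclusions moved the ratio for the primary endpoint, Day 7 AUC0-24. One of the AUC flags can depend on low exposure, so the excluded values need not resemble the kept ones. A report that gives the same ratio twice, the second time labelled as a sensitivity analysis, could be mistaken for evidence of robustness.

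**Working it through.** **The plan's own figure.** The 8.5.2 sentence gives no result to reproduce. The nearest stated figure is the 80% power in section 9.5 (26 evaluable subjects, within-subject CV 43%, true ratio 1.05, limits 0.70 to 1.43). With s_w = √ln(1 + 0.43²) = 0.412, SE = s_w·√(2/26) = 0.114 and df = 24, exact power is 80.1%. It reproduces, and the point does not depend on it.

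**Step 1: which values enter each analysis.**
- Main ANOVA: reliable AUC0-24 values from subjects with one in both periods (8.5.2 with 9.3.3).
- Sensitivity analysis, narrow reading: the same values.
- Sensitivity analysis, generous reading: the same values plus reliable values from subjects with only one usable period. The PK Set leaves room for this.

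**Step 2: the generous reading changes neither ratio nor CI.** Let n subjects have both values and m have one. For the n pairs, let d be the period 1 minus period 2 difference in log AUC0-24. The treatment estimate is (mean d in sequence 1 − mean d in sequence 2) / 2. A subject with one value has no d. That subject's own fixed effect fits the single value exactly, leaving a residual of zero. The residual degrees of freedom are:
- pairs only: 2n − (n + 2) = n − 2
- with single values: (2n + m) − (n + m + 2) = n − 2

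Estimate, residual variance and df are all unchanged, so the 90% CI is unchanged. The geometric LS means can move, but both by the same factor.

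**Step 3: numerical check on simulated data (34 subjects, within-subject CV 43%).**

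| Set-up | Values | Ratio (90% CI) | df |
|---|---|---|---|
| A, pairs only | 52 | 0.964 (0.800–1.161) | 24 |
| A, all reliable values | 60 | 0.964 (0.800–1.161) | 24 |
| A, flagged values retained | 68 | 0.877 (0.726–1.058) | 32 |
| B, pairs only | 54 | 1.0605 (0.8670–1.2971) | 25 |
| B, all reliable values | 58 | 1.0605 (0.8670–1.2971) | 25 |
| B, flagged values retained | 68 | 1.0652 (0.8920–1.2720) | 32 |

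Set-up A assumes 8 subjects flagged in one period, with the flagged value lowered by 1 log unit. Set-up B assumes 7 flagged subjects (3 in both periods, 4 in one) and a between-subject CV of 60%. The table shows B's first data set. Over 500 data sets of type B, the first two rows differed by about 1e-14 at most, which is rounding error. The retained rows show only that such an analysis can differ from the main one. They do not estimate the effect in this trial.

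**Step 4: when the analysis runs.** More than 20% of 34 is more than 6.8, so at least 7 subjects, leaving at most 34 − 7 = 27 complete pairs. More than 20% of 26 is more than 5.2, so at least 6 subjects, leaving at most 20. The threshold is 7 for any denominator from 30 to 34 and 6 for any from 25 to 29. The text does not say which analysis set is counted.

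**Step 5: why the excluded values may differ.** The Schedule of Activities gives 12 samples per profile (pre-dose, every 2 h to 20 h, and 24 h). Fewer than 5 quantifiable means at least 8 of 12 below the LLOQ or missing, which low exposure can cause.

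**The case against.** Section 8.5.2 names no model or analysis set for this check and does not say that only reliable cases are used. With a random subject effect, single-period values would contribute and the result could differ. Details of a conditional supportive analysis are commonly left to the SAP, and 8.5.2 says more will follow there. The likeliest explanation is a drafting slip, since *additionally* makes sense only if unreliable or all cases were meant. Flagged values are also listed, so the exclusions stay visible.

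Much of this stands, and it limits the weight. The identity is conditional on the 9.3.3 ANOVA, but that is the only model the protocol gives for the AUC0-24 ratio, and it has no random subject effect. The SAP argument does not remove the point. The complaint is not that detail is missing: the protocol states which cases define the analysis. An SAP that follows it inherits an empty check, and one that adds the flagged cases departs from it. A listing shows which values were excluded but not what they did to the ratio.

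A reader might also infer that the main AUC0-24 analysis is biased by dropping low-exposure profiles. The documents do not support that: the LLOQ is not given, so neither the frequency of flags nor their effect can be computed. Nor can the identity be extended to Cmax. It has its own unreliability rule, and 9.3.3 does not say whether the restriction to a valid AUC0-24 in both periods carries over. If it does, the reliable Cmax cases could form a different set from the main one.

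**Conclusion.** The point holds, at minor severity. For AUC0-24, the sensitivity analysis defined in 8.5.2 differs from the main Test/Reference ratio and 90% CI by exactly zero, so it cannot show whether the exclusions matter. This rests on two readings: that the analysis uses the 9.3.3 fixed-effects ANOVA, and that *valid* in 9.3.3 means not flagged as unreliable. The primary estimator is not shown to be wrong. How often the check would be triggered cannot be worked out from the protocol.

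**What to change.** In 8.5.2, change the end of the sentence so that the analysis is run *including the unreliable cases (all calculable flagged values retained)*. State that it uses the same ANOVA as 9.3.3 and is supportive, and name the analysis set that forms the denominator of the 20% trigger. AUC0-24 values that section 10.6 sets to missing stay out.

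One consequence needs a rule in advance. Under 8.5.2, "concentrations below the lower limit of quantification (LLOQ) will be treated as zero", so a flagged profile with no quantifiable sample has an AUC of zero and no logarithm. The SAP should say how such a profile is handled in this analysis. No particular convention is prescribed here.

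The cost is a reworded phrase, a sentence or two, and one more run of an existing model. The downside is accuracy. Three or more consecutive missing samples inside a profile leave a gap of at least 8 h for the trapezoidal rule to bridge. With reference applications at 0, 5, 10 and 15 h (Table 6), that gap can span one or two of them. Profiles with few quantifiable values are also poorly determined. The result is therefore a check on robustness and does not replace the main analysis.

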8.6. Pharmacodynamics

PD parameters are not evaluated in this study.

8.7. Genetics

Pharmacogenetics are not evaluated in this study.

8.8. Biomarkers

Biomarkers are not evaluated in this study.

8.9. Immunogenicity Assessments

Not applicable.

8.10. Health Economics or Medical Resource Utilization and Health Economics

Health economics or medical resource utilization and health economics parameters are not evaluated in this study.

9. Statistical Considerations

The statistical analyses will be performed by Nuvisan.

9.1. Statistical Hypotheses

No formal statistical hypotheses have been defined for this systemic bioavailability study.

9.2. Analysis Sets

For purposes of analysis, the following analysis sets are defined:

| Analysis Set | Description |
|----------------|--|
| Screening Set | All subjects screened. |
| Randomized Set | All subjects randomly assigned to study intervention. |
| Safety Set | All subjects randomly assigned to study intervention and who receive at least 1 dose of study intervention. Subjects will be analyzed according to the intervention they actually received. This analysis set will be used for the analysis of safety. |
| PK Set | This analysis set is a subset of the Safety Set and includes all subjects who complete at least one period without any findings/events likely affecting PK. This analysis set will be used for the analysis of PK. |

Finding/events potentially affecting PK will be pre-specified in a deviation manual.

The final decision to exclude complete subjects or single periods of subjects from the PK analysis will be made during a DRM prior to database lock. The respective meeting minutes will be signed together with the Sponsor.

9.3. Statistical Analyses

Statistical analysis will be performed using SAS® and the version used will be specified in the SAP, which will be finalized before database lock. The SAP will contain a more comprehensive explanation than described below of the methodology used in the statistical analyses. The SAP will also contain the rules and data handling conventions to be used to perform the analyses.

Objectives and endpoints are described in Section 3 (Table 4).

9.3.1. Efficacy Analyses

This section is not applicable as efficacy is not assessed in this study.

9.3.2. Safety Analyses

All safety analyses will be performed on the Safety Set.

- Safety data will be listed by subject.
- AEs will be encoded using the MedDRA dictionary, latest version. Summary tables by intervention will be generated for TEAEs (as defined in Section 10.3.1), sorted by system organ class and preferred term, in which the number and percentages of subjects with treatment-emergent AEs and frequency of the events are reported.
- Any AEs that continue but change in severity within a study intervention will be counted as one and only one AE considering the worst severity in frequency tables whereas a recurrent AE (e.g. a headache for a couple of hours each day) will be counted as several AEs.
- AE occurring after administration of any study intervention will be counted towards the last intervention received before the onset, even if the event is not resolved at the beginning of the following intervention. An AE that worsens after a later intervention period will be counted towards both study interventions.
- Laboratory values outside the normal ranges will be flagged. A listing of abnormal laboratory values and clinically relevant abnormal laboratory values will also be provided.
- Descriptive statistics of vital signs and ECG data will be presented for each timepoint by intervention.
- The ECG interpretation of the Investigator will be tabulated as the number and percentage of subjects with “normal”, “abnormal, not clinically significant”, or “abnormal, clinically significant” results by intervention and timepoint.
- The skin irritation scores (i.e., the ‘dermal response score’, see Table 7) will be summarized by application site and treatment. Furthermore, the proportion of subjects with each irritation score will be presented by application site and treatment.

9.3.3. Pharmacokinetic Analyses

- All PK analyses will be performed on the PK Analysis Set, if not stated otherwise.
- Concentration-time courses and PK parameters will be tabulated by intervention.
- The following statistics will be calculated for each of the sampling timepoints: number of cases/ measurements (denoted as “n”), geometric mean and geometric coefficient of variation (CV, in %), arithmetic mean, standard deviation (SD) and CV (in %), minimum, median, maximum.
- Individual and arithmetic mean plasma concentration versus time curves (using the actual sampling times for individual plots and the scheduled sampling times for mean plots) will be plotted by intervention using both linear and log-linear scale.

Further analysis for the primary PK parameter AUC₀₋₂₄:

- In order to achieve a better approximation to a normal distribution, the pharmacokinetic parameters AUC₀₋₂₄ on Day 1 and Day 7 will be logarithmically transformed. Afterwards, they will be evaluated statistically using ANOVA with INTERVENTION, PERIOD, SEQUENCE and SUBJECT(SEQUENCE) as fixed effects. Least-squares (LS) means, LS intervention difference, and 90% confidence intervals (CI) for the intervention differences on the log-scale will be obtained for AUC₀₋₂₄ on Day 1 and on Day 7. The results will be back-transformed to the original scale by exponentiation to provide geometric least-square means, point estimate of the geometric mean ratio (Test/Reference) and its corresponding 90% CI.
- Only subjects that have a valid AUC₀₋₂₄ in both periods will be included in the above-mentioned model.

Further analysis for the secondary PK parameter C_{max}:

- The same ANOVA model as described for AUC₀₋₂₄ above will be provided for the secondary parameter C_{max}.

9.3.4. Other Analyses

Not applicable.

9.4. Interim Analysis

No formal interim analyses will be performed within Nuvisan Biostatistical Department.

9.5. Sample Size Determination

It is planned to assign 34 subjects to study intervention to have at least 26 evaluable subjects completing the study. If deemed necessary to meet the target number of 26 evaluable subjects, dropouts may be replaced (refer to Section 7.2.2).

Based on the assumption (average CV of 3 historical studies), the intra-subject coefficient of variation (CV) was about 43%. A total of 26 evaluable subjects will achieve 80% power, that the 90% confidence interval (CI) is included in the pre-defined acceptance range of 0.7-1.43, which is deemed to be appropriate. The true ratio that was used in the sample size calculation was 1.05. Enough healthy adults will be screened to randomize approximately 34 subjects to ensure 26 evaluable subjects, assuming an approximate 20% dropout and non-evaluable rate.

9.6. Protocol Deviations

- A protocol deviation is any change, divergence, or departure from the study design, or procedures defined in the protocol. Protocol deviations will be identified prior to database lock.

- Important protocol deviations are a subset of protocol deviations that may significantly affect the completeness, accuracy and/or reliability of the study data or that may significantly affect a subject's rights, safety, or well-being.
- Protocol deviations will be pre-specified in a deviation manual, discussed on an ongoing basis and finally categorized as important/non-important during the DRM. A protocol deviation may also be declared as finding/event that leads to an exclusion of data or complete subjects from an Analysis Set (see Section 9.2).
- Important protocol deviations will also be described in the CSR.

9.7. Data Management

Nuvisan will be responsible for clinical data management activities for this study. The full details of procedures for data handling will be documented in the Data Management Plan.

Medical coding will be done using the latest version of the coding dictionaries for MedDRA for AEs and medical history to the primary SOC and WHO Drug Global Dictionary for concomitant medications. Coding will be performed by Data Management and needs to be approved by the Investigator and Sponsor.

9.7.1. Database Lock

Study database must be soft and hard locked to ensure their integrity for the generation of results, analysis and submissions.

9.7.2. Soft Lock

When validation (including external data reconciliation), SAE reconciliation and all coding activities, as well as medical review activities, QC activities have been completed and there are no further open issues or open queries the database will be soft locked.

9.7.3. Data Review Meeting

A DRM will be held for the study by the biostatistician to check the data status, discuss any open issues and provide proposals for resolution, as well as finally agree on the categorization of the protocol deviations and assignment of subjects to analysis sets.

9.7.4. Hard Lock

After finalization and approval of the DRM minutes, and after all actions resulting from the DRM minutes are completed, e.g., additional solving of queries, the database will be hard locked. Hard lock needs to be authorized by the study team.

9.7.5. SDTM and ADaM Conversion

The database and the electronic external data will be converted to CDISC / SDTM and ADaM.

10. Supporting Documentation and Operational Considerations

10.1. Appendix 1: Regulatory, Ethical, and Study Oversight Considerations

Before the start of the study, Nuvisan on behalf of the Sponsor will apply for approval for the performance of the study at the CA (German Federal Institute for Drugs and Medical Devices [BfArM]) and the IEC.

10.1.1. Regulatory and Ethical Considerations

- This study will be conducted in accordance with the protocol and with the following:
 - Consensus ethical principles derived from international guidelines including the Declaration of Helsinki and Council for International Organizations of Medical Sciences International Ethical Guidelines
 - Applicable ICH GCP Guidelines
 - Applicable laws and regulations
- The protocol, modifications to the protocol (modifications), ICF, IB, and other relevant documents (e.g., advertisements) must be submitted to an IEC and reviewed and approved by the IEC before the study is initiated.
- Any substantial modification to the protocol (substantial modification) will require CA and IEC approval before implementation of changes made to the study design, except for changes necessary to eliminate an immediate hazard to study subjects.
- The Investigator will be responsible for the following:
 - Notifying the IEC of SAEs or other significant safety findings as required by IEC procedures
 - Providing oversight of the conduct of the study at the site and adherence to ICH guidelines, the IEC, European Regulation 536/2014, and all other applicable local regulations
 - Performing a benefit-risk assessment on an ongoing basis and informing the IEC about any changes. Moreover, making sure that any substantial modifications to the protocol (substantial modifications) will be submitted and approved prior to implementation

